Biochemistry blood test: Sodium (Na), Potassium (K), Chloride (Cl), Creatinine, Glucose, Urea, Albumin, Calcium total, Alkaline Phosphatase (ALP), ALT, AST, Total Bilirubin, Direct Bilirubin, LDH, Total Protein, Uric Acid, CRP, and Lipid Profile (including Total Cholesterol, HDL, LDL, Triglycerides).

Hematology blood test: complete CBC.

D-Dimer test (coagulation): one tube for coagulation test

Inflammatory markers: the blood will be centrifuged and frozen according to the Lab manual, Local Lab.

Vital signs: blood pressure, pulse, weight, weight, body temperature (PO), saturation, respiratory rate.

VAS scale: will be performed by study staff member.

WHO Ordinal Score: will be completed by the study staff member based on patient status.

COVID-19-Related Symptoms assessment: will be completed by the study staff member based on patient status and answers.

COVID-19–Impact on Quality-of-Life Questionnaire: will be completed by the study staff member based on patient answers.

	MGC Pharma Clinical Study Protocol	Protocol No.: MGC-009
		Version 02, 05 Sep 2021
		Page 40 of 76
A Phase IIb, double blind, placebo-controlled clinical study designed to evaluate the effect of CimetrA in patients diagnosed with COVID-19		CONFIDENTIAL

POST- COVID-19 Functional Status Scale: will be completed by the study staff member based on patient answers.

Pregnancy test: women of childbearing potential must undergo a urine pregnancy test.

Physical examination: full examination by doctor.

** Measurements will be performed per institutional schedule by the hospital staff, not necessarily by the principal investigator or the sub-investigators.

PK parameters*: will be performed only on 14 patients that will agree to participate in the PK analysis (only for Brazil and South Africa).

The PK will be performed only for the first dose of drug, after patient received the first dose (5 puffs) the study staff need to follow the table below.

For each test, approximately 5 ml of blood will be drawn (equivalent to one teaspoon) total of 55 ml of blood will be drawn.

Table 6: List of time points for pharmacokinetic assessments

Study Visit Number 1	
Time point 0	Dosing (before the first dose of the drug)
Time Point 1	15 minutes post dose
Time Point 2	30 minutes post dose
Time point 3	45 minutes post dose
Time point 4	1 h post dose
Time point 5	1.5 h post dose
Time point 6	2 h post dose
Time point 7	4 h post dose
Time point 8	6 h post dose
Time point 9	8 h post dose

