12.1. STUDY DRUG DOSAGE AND ADMINISTRATION

The study drug dosage groups are defined based on the preclinical and clinical experience with CimetrA.

Arms 1 and 2 doses were defined based on the preclinical data, presented in the Investigator Brochure, when CimetrA formulation demonstrated an anti-inflammatory activity in lower dosages. The rationale of additional dosage is based on the potential ability of CimetrA to be active in different ways in prevention of deterioration of COVID-19 patients. As per FDA's requirement for the dose finding, additional study arm dosage was defined based on the preclinical studies described above.

Minor dose adjustment was performed according to the CMC limitation as a result of the nano-particles characteristics.

Arm 1: CimetrA-1, with a total dose containing a combination of Curcuma longa rhizome dry extract 28 mg, Boswellia serrata resin dry extract 60 mg in spray administration – divided in 4 separate doses given as an add on therapy, total of 4 doses over 48 hours (day 1 and day 2), twice a day (morning and evening).

Single dose: 1ml of dose contain Curcuma longa rhizome dry extract 7 mg/ml, Boswellia serrata resin dry extract 15 mg/ml in spray administration , for one dose are required 5 puffs from the study drug spray.

Daily dosage is 2 ml which equal to 10 puffs from the study drug spray.

Arm 2: CimetrA-2, with a total dose containing a combination of Curcuma longa rhizome dry extract 19.6 mg, Boswellia serrata resin dry extract 42 mg in spray administration – divided in 4 separate doses given as an add on therapy, total of 4 doses over 48 hours (day 1 and day 2), twice a day (morning and evening).

	MGC Pharma Clinical Study Protocol	Protocol No.: MGC-009
		Version 02, 05 Sep 2021
		Page 50 of 76
A Phase IIb, double blind, placebo-controlled clinical study designed to evaluate the effect of CimetrA in patients diagnosed with COVID-19		CONFIDENTIAL

Single dose: 0.7 ml of dose contain Curcuma longa rhizome dry extract 4.9 mg/ml, Boswellia serrata resin dry extract 10.5 mg/ml in spray administration, for one dose are required 5 puffs from the study drug spray.

Daily dosage is 1.4 ml which equal to 10 puffs from the study drug spray.

Arm 3: Placebo, composed of the same solvent but without active ingredients, given as an add on therapy in spray administration, total of 4 doses over 48 hours (day 1 and day 2), twice a day (morning and evening).

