Patients will be randomized in 1:1:1 ratio to one of the three arms.

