Sample size and Power were calculated with the Power and Precision statistic program ver 4.1 and all statistical analyses and data presentations, including tabulations and listings, will be performed using the SPSS statistic program version 27.0 (or higher) software.

Randomization

Randomization tend to produce study groups comparable with respect to known and unknown risk factors, removed investigator bias in the allocation of participants and guarantees that statistical tests will have valid false positive error rates.

After a participant will meet the eligibility criteria, he/she will be randomly allocated (with a 1:1:1 ratio) to one of the following treatment groups based on a randomization scheme stratified by center.

The randomization scheme will be prepared by an independent statistician using statistic program for random number generator. The block size is set in ahead and study personnel will be blinded to the randomization block size.

Blinding

This is a double-blind study: neither the participants nor the investigators will be aware of arm allocation of each study participant.

Blindness is important to avoid bias. Monitoring and reporting of the success of blindness are important for the reader's confidence of the trial results. Groups should be marked by capital letter and blindness should maintain throughout the study.

Missing Data

Safety data should be collected from non-adherent/withdrawal participants to avoid possible bias.

	MGC Pharma Clinical Study Protocol	Protocol No.: MGC-009
		Version 02, 05 Sep 2021
		Page 62 of 76
A Phase IIb, double blind, placebo-controlled clinical study designed to evaluate the effect of Cimetra in patients diagnosed with COVID-19		CONFIDENTIAL

Prior to analyzing the data, extreme laboratory values should be checked. Missing values will be treated as ITT.

Multiple imputation for binary data will be used as the primary imputation method in the case of missing data for the primary efficacy endpoint.

Dropout/AE Imputation: A participant with no post baseline measurement or a participant withdrawn due to an adverse event or treatment intolerability will use last observation carried forward imputation methods.

Baseline Data

Baseline participant characteristics will be collected at screening. The specific baseline (“start of treatment”) endpoints and other symptoms will be collected prior to each treatment.

Significance Levels and Handling of Type I Error

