A Phase IIb, double blind, placebo-controlled clinical study designed to evaluate the effect of CimetrA in patients diagnosed with COVID-19		CONFIDENTIAL

The 3 groups will be compared with the ANOVA test or Kruskal Wallis non-parametric test, following by post-hoc analysis for pairs differences.

Additional Efficacy Parameters of Interest

A count and percentage of participants responding to each of the exploratory efficacy endpoints will be presented. The groups will be compared with a chi-squared test or a Fisher’s exact test.

Safety Analysis

The primary safety variable, the cumulative incidence (and 95% CI) of device related adverse events (AEs) throughout the study, will be presented in tabular format and will include incidence tables by severity.

Serious adverse events, device-related SAEs, adverse events (by type and overall), device-related AE, adverse device reactions and device malfunction rates will be compared between the study arms with a Fisher’s exact test.

Serious adverse events will be listed and discussed individually.

PK test

Actual times of dosing and blood collection at various time points will be recorded in source documents as well as CRF’s. Objectives of PK sampling are to measure values of CimetrA active ingredients in plasma at different time point after first administration of study medications and at different time point after multiple administrations during steady state.

PK samples will be processed and frozen on site. Labels have been prepared for the site again containing patient No., visit No., type of test (PK) and time point. Upon completion of the study, samples will be sent to selected analytical laboratory with dedicated courier service. The PK parameters will be obtained from plasma concentration data for curcumin and boswellia.

	MGC Pharma Clinical Study Protocol	Protocol No.: MGC-009
		Version 02, 05 Sep 2021
		Page 65 of 76
A Phase IIb, double blind, placebo-controlled clinical study designed to evaluate the effect of Cimetra in patients diagnosed with COVID-19		CONFIDENTIAL

Analyses of PK data will be based on the PK Set, which will include all subjects who received at least one treatment and for whom concentration data is available.

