Plasma concentration data will be tabulated and plotted for each subject for whom concentrations are quantifiable and for each treatment group. Actual times of sample collection will be used. PK analysis will be performed using appropriate non-compartmental techniques to obtain estimates of the following standard PK parameters if deemed possible:

- Maximum observed serum drug concentration (C_{max})
- Time to C_{max} (t_{max})
- Lag time to start of absorption (T_{lag})
- Area under the plasma drug concentration-time curve (AUC) from time 0 to the last quantifiable concentration (AUC_{0-t})
- AUC from time 0 to infinity ($AUC_{0-\infty}$)
- Percentage of $AUC_{0-\infty}$ extrapolated (AUC_{ext})
- Apparent total volume of distribution at the terminal phase (V_z/F)
- Apparent total body clearance (CL/F)
- Terminal elimination rate constant (λ_z)
- Apparent terminal elimination half-life ($t_{1/2, z}$)
- Dose normalized C_{max} , $AUC_{0-\infty}$, AUC_{0-t}

Details of storage, handling and shipping of blood samples will be described in a Laboratory Manual.

Randomization and stratification.

	MGC Pharma Clinical Study Protocol	Protocol No.: MGC-009
		Version 02, 05 Sep 2021
		Page 66 of 76
A Phase IIb, double blind, placebo-controlled clinical study designed to evaluate the effect of Cimetra in patients diagnosed with COVID-19		CONFIDENTIAL

Subjects would be assigned in sets of four as one per each of the four study groups – this would assure that we maintain exact balance among groups in terms of n / group.

Stratification will be performed according to the medical history and risks factors, based on the data will be received in the study.

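### The 14 PK patients have no allocation by arm, so one active dose may end with three or fewer concentration profiles

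*Protocol*

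**What the plan says.** - Section 8 lists pharmacokinetics among the study's purposes, and Section 9.2 makes the PK profile a secondary outcome.
- Notes to Table 5 (Section 10.2.1): PK "will be performed only on 14 patients that will agree to participate in the PK analysis (only for Brazil and South Africa"). No number per arm is given, and sampling is not confined to the active arms.
- Section 12.1: "Patients will be randomized in 1:1:1 ratio to one of the three arms". One of the three arms is placebo.
- Section 17, Randomization: allocation is "based on a randomization scheme stratified by center", with a block size fixed beforehand and hidden from study staff. A later paragraph of the same section says "Subjects would be assigned in sets of four as one per each of the four study groups", although there are three groups.
- Section 17, PK test: "The PK parameters will be obtained from plasma concentration data for curcumin and boswellia". Results are tabulated and plotted by subject and by treatment group. The parameters include "Apparent total body clearance (CL/F"), Vz/F and dose-normalised Cmax and AUC. The PK Set does not exclude placebo patients. No test between doses is planned.
- Section 12.1 gives doses only as mg of dry extract, for example "Single dose: 1ml of dose contain Curcuma longa rhizome dry extract 7 mg/ml".

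**The concern.** Two active doses are studied, and Section 12.1 gives dose finding as a reason for the second. The PK subset is the only part of the trial that shows what exposure each dose produces. Its 14 patients are whoever volunteers in two countries, and chance decides which arm they are in. Because the trial is double blind, sites cannot steer PK recruitment towards a thin arm. If one dose ends with two or three profiles, even a descriptive group summary says little about exposure at that dose. No analysis plan can repair this once patients are randomised, so it has to be settled in the protocol.

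The PK paragraph also leaves open what is measured in plasma for Boswellia and which dose enters the dose-scaled parameters.

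**Working it through.** **Inputs.** m = 14 PK patients (notes to Table 5); allocation probability 1/3 per arm (12.1); stratification by centre with undisclosed block size (17). The protocol gives no derivation for 14, so there is no figure of the plan's own to reproduce.

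**Expected split.** 14/3 = 4.67 per arm: about 9.3 patients on active drug and 4.7 on placebo.

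**Independent allocation.** The number in one active arm is binomial(14, 1/3). By inclusion–exclusion, P(at least one active arm ≤ t) = 2·P(one arm ≤ t) − P(both ≤ t).

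- t = 3: 2 × 0.2612 − 0.0245 = 0.498
- t = 2: 2 × 0.1053 − 0.0018 = 0.209
- P(placebo ≥ 6) = 0.310

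The expected size of the smaller active arm is 3.45.

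**Allocation blocked within centre.** Block size, number of PK centres and consent rate are not in the protocol, so these are assumptions. Simulation took blocks of 3 or 6, two or four PK centres sharing the 14 as evenly as possible, and each patient consenting independently:

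| Consent | P(an active arm ≤ 3) | P(an active arm ≤ 2) |
|---|---|---|
| 30% | 43–45% | 14–16% |
| 50% | 37–40% | 9–12% |
| All consecutive patients | 0–33% | 0–7% |

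In the last row the only non-zero case is blocks of 6 over four centres. There the centres contribute 4, 4, 3 and 3 PK patients, so no block is completed. In the other three cases the completed blocks alone guarantee 4 per arm. With six centres and full consent, P(≤ 3) is 22% for blocks of 3 and 43% for blocks of 6.

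**One shared PK list.** With blocks of 3, 14 = 4 × 3 + 2. Each arm gets 4, and two arms get one more, so the split is 5:5:4 in some order. With blocks of 6, 14 = 2 × 6 + 2. Each arm gets 4, and the last two places give a range of 4 to 6. No arm falls below 4 in either case.

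**Arm 2 dose (12.1).**

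| Extract | Total over 4 doses ÷ 4 | Single dose, volume × concentration |
|---|---|---|
| Curcuma | 19.6/4 = 4.9 mg | 0.7 × 4.9 = 3.43 mg |
| Boswellia | 42/4 = 10.5 mg | 0.7 × 10.5 = 7.35 mg |

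The ratio is 4.9/3.43 = 1.43 for both extracts. It would pass directly into the Arm 2 dose-normalised values, CL/F and Vz/F.

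**The case against.** **Centre blocks already protect the split.** This stands in part. If PK patients are consecutive and come from few centres, four or five per arm is likely, and 50% is an upper figure, not the expected case. But PK patients are volunteers who accept repeated blood draws, and the Day 1 list requires PK to be done before standard of care. Once some patients decline, blocking helps little. The block text is also contradictory: sets of four for four groups in a three-arm trial.

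**The PK output is descriptive.** True: estimates are produced where possible and no dose comparison is tested. A reader might infer that a planned comparison of doses will rest on two or three patients; the protocol supports neither a planned test nor that certainty. The consequence is a possibly uninformative group summary.

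**Clearance and volume are mis-scaled.** A reader might infer this because doses are in mg of extract while plasma curcumin is measured. The documents do not support it. Section 17 never says that extract mass is the divisor, and Section 12.2 foresees composition data from the Certificate of Analysis. The dose term and assay analytes are commonly fixed in an analysis or bioanalytical plan, which is not shown. Cmax, tmax, AUC and half-life do not use dose, and a common content factor cancels between the two doses if both use the same extract. With no content given, no size of error can be stated.

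**The remedy still samples placebo patients.** Correct: a blocked list secures the number of profiles per dose but does not reduce placebo sampling.

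**Conclusion.** The point holds as a gap in the allocation of the PK subset. As written, nothing guarantees a usable number of profiles at each dose. The chance that an active dose has three or fewer is 50% if consenters are allocated independently. It is about 37–45% with centre blocks of 3 or 6 in two or four centres at 30–50% consent, and 0–33% in those centres if everyone consents. For two or fewer, the figures are 21%, 9–16% and 0–7%. The 50% and 21% rest only on 14 patients and a 1:1:1 ratio; the others depend on the assumed block size, centre number and consent rate.

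The unnamed Boswellia analyte and the unstated dose term are a minor drafting note, not a demonstrated error. The Arm 2 single-dose conflict is a real contradiction within Section 12.1, of 1.43-fold, and those passages must be reconciled.

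**What to change.** 1. In Sections 10 and 17, require PK consent before randomisation. Allocate PK consenters from one separate blocked list shared by the Brazilian and South African PK centres, with block size concealed from sites, until 14 are randomised. The split is then about 5:5:4 by design. Correct the sets-of-four sentence at the same time.
2. In the PK test paragraph, name the boswellic acid(s) measured, and state that analyte mass is the dose used for CL/F, Vz/F and dose-normalised Cmax and AUC.
3. Reconcile the Arm 2 volume, concentration and total-dose statements in 12.1 before any dose-normalised value is computed.

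**Cost.** One extra randomisation list and some protocol wording, with no added patients or samples. A list shared across centres needs central release of allocations. Within-centre balance becomes slightly looser, for 14 of 240 patients (14/240 = 5.8%). Four or five placebo patients will still give PK samples.

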18. DATA MANAGEMENT

Data management based on GCP refers to the activities defined to achieve safe routines to enter subject information into a database efficiently and with avoiding of errors.

The data management routines include procedures for handling of CRFs, database and data entry screens set-up, validation of the database and data entry screens, data entry and verification, and documentation of the performed activities including information of discrepancies in the process. The database, data entry screens and programs will be designed in accordance with the study protocol and the CRF.

The Clinical Monitor will check entries in the CRF data from the site. The data are exported to a clinical database. Logical checks programs will systematically check the clinical database and obvious errors will be corrected.

Findings from visual and automated logical checks will be compiled on Data Clarification Forms (DCF) per each Subject. The DCF will be sent to the site for resolution. The signed DCF will be returned to MGC-Pharma. The error resolutions/data clarifications (query resolution process during the study) will be entered into the clinical database. When a clean file has been accomplished, the database will be locked after a formal clean file procedure.

The computerized data processing will be the responsibility of MGC-Pharma using standard software. The statistical analysis will be performed by MGC-Pharma or a

	MGC Pharma Clinical Study Protocol	Protocol No.: MGC-009
		Version 02, 05 Sep 2021
		Page 67 of 76
A Phase IIb, double blind, placebo-controlled clinical study designed to evaluate the effect of CimetrA in patients diagnosed with COVID-19		CONFIDENTIAL

consultant approved by MGC-Pharma. Data will be processed in agreement with local legislation and accepted practice.

19. **CHANGES IN THE APPROVED STUDY PROTOCOL**

Any proposed protocol change must be discussed with and approved by MGC-Pharma and the Investigator before submitted to IEC/IRB and Regulatory Authority, for approval or notification according to applicable national regulations. Substantial protocol changes should be documented in a written and numbered Protocol Amendment, which must be signed and dated by the same parties who signed the Final Study Protocol.

20. **CURRICULUM VITAE**

A Curriculum Vitae (CV) must be obtained from all Investigators and staff members carrying out observations of primary or other important variables involved in the study. It should include name, title, occupation, education, and research experience, present and former positions and should be signed and dated.

21. **PROCEDURES IN CASE OF MEDICAL EMERGENCY**

The Investigator is responsible for ensuring that there are procedures and expertise available to cope with medical emergencies during the study.

21.1. **Emergency contact between Investigator/Monitor/MGC-PHARMA**

If a need for emergency contact arises, Principal Investigator or, if unavailable, MGC-Pharma's Clinical Monitor should be contacted. Although a message may be left with a voice mailbox, the search must nevertheless continue until direct contact is established and the emergency message has been communicated to the appropriate person. The Investigator should provide the study subjects with an emergency contact hospital telephone number.

	MGC Pharma Clinical Study Protocol	Protocol No.: MGC-009
		Version 02, 05 Sep 2021
		Page 68 of 76
A Phase IIb, double blind, placebo-controlled clinical study designed to evaluate the effect of CimetrA in patients diagnosed with COVID-19		CONFIDENTIAL

22. DISCONTINUATION OF THE STUDY

MGC-Pharma reserves the right to discontinue the study at any time, but intends only to exercise this right for valid scientific or administrative reasons.

In the case of overdose, treatment with antiviral therapy will have to be discontinued and the participant should be carefully monitored for potential adverse events and receive appropriate medical treatment according to their clinical condition.

23. FINAL STUDY REPORT AND PUBLICATION OF STUDY RESULTS

After completion of the study, Statistician will perform the statistical analysis. The results will be presented to and discussed with the Investigators as soon as possible. Based on these discussions, MGC-Pharma will prepare a Clinical Study Report. It is agreed between the Investigators and MGC-Pharma that data from the study will be used in connection with the development of the study product.

Information about the study may therefore be disclosed by MGC-Pharma to MGC-Pharma's scientific advisers, Board of Directors, the public, Regulatory Authorities, and others.

The final report will be submitted to Regulatory Authorities and could also form the basis for a manuscript intended for publication in a medical journal, as separately agreed between MGC-Pharma and the Investigators and subject to approval by mutual consent.

Record retention

The Investigator must arrange for retention at the investigational site of a list of the subjects and their identifying codes, subject files and other study documents as hard-copy and electronic files as applicable according to applicable regulatory requirements for:

	MGC Pharma Clinical Study Protocol	Protocol No.: MGC-009
		Version 02, 05 Sep 2021
		Page 69 of 76
A Phase IIb, double blind, placebo-controlled clinical study designed to evaluate the effect of CimetrA in patients diagnosed with COVID-19		CONFIDENTIAL

1. at least two years after the last approval of a marketing application in the EU and US and until there are no pending or contemplated marketing applications in the EU and US; or
2. at least two years have elapsed since the formal discontinuation of clinical development of the investigational product.

The study documents include IEC approvals, the study protocol and all its amendments, all source documents and laboratory records, copies of Case Report Forms, subject informed consent forms, and any other pertinent study document. It is the responsibility of MGC-Pharma to inform the Investigator/institution as to when these documents no longer need to be retained.

Alternatively, the source documents may be stored at a safe place outside the study site after agreement between the Investigator and MGC-Pharma.

Disclosure and confidentiality

